### **8.2 Secondary Objectives**

In patients with HDA-RRMS who initiated on cladribine tablets, overall and by most recent DMT prior to cladribine tablets initiation (DMT naïve, "platform" treatment, high-efficacy cell-depleting treatment, or high-efficacy non-depleting treatment):

- To analyse the proportion of patients relapse-free at each year (and up to 5 years) after cladribine tablet initiation
- To analyse the time after cladribine tablet initiation to first relapse
- To evaluate the proportion of patients who discontinued cladribine tablets and reasons for discontinuation
- To evaluate the subsequent DMT received after cladribine tablets discontinuation up to 5 years after cladribine tablets initiation
- To analyse the proportion of patients with disability progression confirmed over 6 months, 2 years after treatment initiation
- To analyse the incidence rate of selected, identified, and potentially clinically important adverse events (AEs)

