### 9.1.2.2 Secondary

- Proportion of patients who remain relapse-free in each year and at 4 and 5 years after initiation of cladribine tablet treatment
- Time from cladribine tablet initiation to first relapse
- Proportion of patients who discontinued cladribine tablets and reasons for discontinuation
- Subsequent DMTs (none or by DMT type) received after cladribine tablets discontinuation/treatment completion up to 5 years after cladribine tablets initiation
- Disability assessed by the EDSS at treatment initiation and start of treatment Year 2

The EDSS is a neurological assessment to evaluate disability in patients with MS, performed by the physician. The annual EDSS at cladribine tablet treatment initiation and start of treatment Year 2 will be recorded, where available in the patients' notes. EDSS is routinely collected as part of standard care in the UK as part of the annual assessment required for continuation of treatment.

- Proportion of patients with disability progression confirmed over 6 months, assessed by the EDSS, at 2 years after cladribine tablet treatment initiation

An EDSS progression is defined as an increase in the EDSS scale as follows:

- If the EDSS score at cladribine tablet initiation is 0, the increase must be  $\geq 1.5$  units
- If the EDSS score at cladribine tablet initiation is  $\geq 0.5$  or  $\leq 4.5$ , the increase must be  $\geq 1.0$  units
- If the EDSS score at cladribine tablet initiation is  $\geq 5.0$ , the increase must be  $\geq 0.5$  units.

A confirmed disability progression is defined as EDSS progression (as defined above) confirmed after 6 months.

- Rates of selected, identified, and potentially clinically important AEs, including:

- grade 3 lymphopenia
- grade 4 lymphopenia
- herpes infections
- serious infections (infections for which a hospitalisation is initiated or extended)
- opportunistic infections (new onset or reactivation of latent infection)
- malignancies

These AEs will be reported from the date of cladribine tablet initiation and will be described overall and by most recent prior DMT subgroups (DMT naïve, prior platform treatment, prior high-efficacy cell-depleting treatment, and prior high-efficacy non-depleting treatment).

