## **9.5 Study Size**

Approximately 200 patients will be enrolled in this study, with a minimum of 90 patients. This sample size is based on an estimation of what is feasible during the study period. The study will not be powered to detect or report statistical differences and has no comparator group. It will be qualitative and descriptive in nature.

With an expected annualised relapse rate of 0.14 over 2 years ([Giovannoni 2010](#)), the distance from proportion to limit of the corresponding 95% confidence interval (CI) will be 0.072 based on available data for 90 patients.

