#### Primary Outcome Analysis

The annualised relapse rate for a patient is defined as the number of clinician's confirmed relapses that occurred in the year prior to the date of cladribine tablet initiation, and in Years 1, 2, 3, 4 and 5 after treatment initiation with cladribine tablets (upon availability, depending on the available observation time):

- Year prior to date of cladribine tablet initiation: Month -12 to the day before the date of cladribine tablet initiation (Start Month 1)
- Year 1: Start Month 1 to End of Month 12
- Year 2: Start Month 13 to End of Month 24
- Year 3: Start Month 25 to End of Month 36
- Year 4: Start Month 37 to End of Month 48
- Year 5: Start Month 49 to End of Month 60

Relapses will be counted for the defined time period if the date of onset of the relapse is within the defined time period. In the analyses defined in the IAP, an "induction period" after treatment initiation may be considered for the annualised relapse rate in Year 1.

The annualised relapse rate for a patient will be calculated by dividing the number of clinician confirmed relapses during the period by the person-years of the patient (i.e., the period [in days] that a patient was observed in the study divided by 365.25).

The estimated annualised relapse rate in each of the defined years above will be summarised using descriptive statistics for continuous variables.

The annualised relapse rate will be described overall and among the subgroups by most recent prior DMT, as defined in [Table 2](#).

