#### Secondary Outcome Analysis

The proportion of patients who remain relapse-free in each year after treatment initiation (among patients active at start of each year), at 4 years after treatment initiation and at 5 years after treatment initiation (among patients with 5 years observation time available), and the time from cladribine tablet initiation to first relapse will be described using Kaplan-Meier method. Kaplan-Meier survival curve will be plotted (overall and by most recent prior DMT subgroup) and a table with the probabilities of remaining relapse-free in each year after initiation of treatment will be produced.

The proportion of patients who discontinued cladribine tablets and reasons for discontinuation will be summarised using descriptive statistics.

Subsequent DMTs (none or by DMT type) received after treatment with cladribine tablets will be described up to 5 years after cladribine tablet initiation. The proportion of patients who did not receive any other DMT up to a total of 4 years and up to a total of 5 years (among patients with 5 years observation time available) after cladribine tablet treatment initiation will be analysed using descriptive statistics. Depending on the availability of data and the missing data pattern, a survival analysis may be performed to account for loss to follow-up patterns.

The annual EDSS scores at treatment initiation and start of cladribine tablet treatment at Year 2 will be summarised using descriptive statistics. The proportion of patients with disability progression confirmed over 6 months at 2 years after cladribine tablet initiation will be summarised using descriptive statistics.

The number and percentages of patients with AEs will be reported, and the number of AEs itself. The incidence rates of AEs will be summarised by system organ class and preferred term using the Medical Dictionary for Regulatory Activities (MedDRA). Additional summaries will be presented by severity. The AEs will be reported overall, and as stratified in the last prior MS DMT subgroups (as defined in [Table 2](#)).

CCI

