15.1 Adverse Events

The Treatment-Emergent Adverse Event (TEAE) are those events with onset dates occurring within the full treatment period as defined in Section 9.7.

The AEs related to study treatment are those events with relationship missing or “Related”.

All analyses described in this section will be based on TEAEs if not otherwise specified. The AE listings will include all AEs (whether treatment-emergent or not). AEs outside the on-treatment period will be flagged in the listings.

Unless otherwise specified, TEAEs will be summarised by number and percentage of patients with the TEAE in the category of interest, primary SOC and PT in decreasing frequency.

Each participant will be counted only once within each SOC or PT. If a participant experiences more than one AE within a SOC or PT for the same summary period, only the AE with the strongest relationship or the worst severity, as appropriate, will be included in the summaries of relationship and severity.

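### The SAP drops the protocol's planned count of AEs and reports the AE incidence rate, a secondary objective, only as percentages of patients, without declaring a change

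*SAP*

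**What the plan says.** **Protocol.** Section 8.2 lists as a secondary objective "To analyse the incidence rate of selected, identified, and potentially clinically important adverse events". Section 9.1.2.2 turns this into a secondary outcome: "Rates of selected, identified, and potentially clinically important AEs, including" lymphopenia of grades 3 and 4, several kinds of infection, and malignancies. The secondary analysis text in 9.7.3 then plans the outputs. First: "The number and percentages of patients with AEs will be reported, and the number of AEs itself". Next: "The incidence rates of AEs will be summarised by system organ class and preferred term". Results are to be shown overall and by most recent prior DMT.

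**SAP.** Section 5 restates the objective with *incidence* in place of *incidence rate*. It pairs the objective with patient counts and percentages, overall and by PT and SOC. Section 15.1 gives the general rule: "TEAEs will be summarised by number and percentage of patients with the TEAE in the category of interest". A participant contributes at most one count to any SOC or PT. All the tables in 15.1.1 follow that form, and individual events appear only in listings. Section 7 states that the protocol's analyses are unchanged.

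**The concern.** The SAP governs what is programmed. Followed as written, it omits one output that the protocol plans in so many words, the number of AEs. It also reports a secondary safety objective worded as a rate as a crude percentage. A reader of section 7 would conclude that neither had happened.

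Three things are at stake:

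- **Unequal time at risk.** The TEAE window in SAP 9.7 runs from Day 1 to cut-off or death, and patients started cladribine at different times before enrolment. A percentage puts shorter and longer follow-up together without showing it, both overall and when the prior-DMT groups are read side by side.
- **Repeat events.** A patient with several herpes infections counts the same as a patient with one, and no table gives the total.
- **Labelling.** SAP section 4 requires analyses outside the SAP to be identified in the study report as post hoc or unplanned. Event counts or rates added later would carry that label although the protocol planned them.

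**Working it through.** **Step 1. The plan's own figure.** The documents give no expected AE frequency. The only precision figure is in protocol 9.5, for an expected annualised relapse rate of 0.14 and 90 patients: "the distance from proportion to limit of the corresponding 95% confidence interval (CI) will be 0.072".

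- As a proportion: 1.96 × √(0.14 × 0.86 / 90) = 0.0717, which rounds to the stated 0.072.
- As a Poisson rate over 90 person-years: 1.96 × √(0.14 / 90) = 0.077.

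The figure reproduces, and it was computed as for a proportion. It has no bearing on which AE outputs are planned. It does show that the protocol can use *rate* loosely, which matters in step 3.

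**Step 2. Planned outputs against SAP outputs.**

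| AE output | Protocol | SAP |
|---|---|---|
| Patients with AEs, n (%) | 9.7.3 | Sections 5, 15.1, 15.1.1 |
| Number of AEs | 9.7.3 | In no table; listings only |
| Incidence rate | 8.2, 9.1.2.2; by SOC/PT in 9.7.3 | Not mentioned; section 5 says *incidence*, measured as n (%) |
| Declared change | – | Section 7: none |

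**Step 3. How certain is each gap?**

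*Event count.* Certain. The protocol names it separately, and the once-per-participant rule means that no table cell can be read as a number of events.

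*Rate.* Probable. The protocol gives n (%) in one sentence and incidence rates in the next, so reading the second as a percentage makes it largely repeat the first. The protocol's one explicit rate formula, for relapses, divides "by the person-years of the patient (i.e., the period [in days] that a patient was observed in the study divided by 365.25". Against this, the visible protocol text attaches no denominator to the AE rate, and loose usage occurs elsewhere: step 1, and SAP 14.2.1, where a relapse-free rate is defined as a time.

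**Step 4. Spread of follow-up.** Protocol 9.2.3 gives an observation period of 5 to 7 years, including 1 year before initiation. Planned time at risk is therefore 5 − 1 = 4 to 7 − 1 = 6 years, a ratio of 6 / 4 = 1.5 between the longest and the shortest. This describes the planned range. It is not an estimate of bias.

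**Step 5. Is there a person-time rule that AEs could borrow?** The only one is in SAP 14.1.1, for the annualised relapse rate, and it stops at the last-contact date of SAP 9.5. Nothing applies it to AEs.

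**The case against.** The strongest defence is that the SAP does say what it measures. Section 5 pairs the objective with n (%) of patients, and section 15 carries that through. This stands, and it rules out a stronger reading that a reader might infer, namely that the SAP leaves the AE measure undefined. The fair complaint is an undeclared choice of measure.

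Other points also carry weight:

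- The relapse formula in protocol 9.7.3 is a per-patient rate that is then summarised as a continuous variable. It supports person-time as the protocol's idea of a rate, but it does not prescribe a pooled AE rate.
- Protocol 9.7.3 has redacted text directly after the AE paragraph, so the missing denominator can be asserted only of what is visible.
- The study is descriptive, with no comparator and no hypothesis test, and the planned follow-up range is moderate.
- Where events cluster early, a percentage stays stable while a rate falls as follow-up lengthens. A rate should therefore stand beside the percentages and not replace them.
- All AEs are listed, so the events could be counted.

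None of this removes the mismatch. A listing is not the planned summary. The loose reading of *rate* does nothing for the missing event count. Under either reading, a statement that nothing changed is inaccurate for at least one planned output.

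**Conclusion.** The point holds. The planned number of AEs is absent from every SAP table, without qualification. The AE incidence rate is absent on the natural reading of the protocol, with the residual doubt set out in step 3. SAP section 7 declares neither.

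No numerical size can be given. It would depend on AE frequencies, repeat events and the distribution of follow-up by group, and the documents supply none of these.

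Three further inferences are not supported:

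- *That the percentages are biased by a known amount, or distort the comparison of prior-DMT groups.* The documents show no difference in follow-up between those groups.
- *That the single SAP row for serious and opportunistic infections is part of the same departure.* Protocol 9.1.2.2 lists them apart, but protocol 9.3 puts them in one bullet. That is a separate matter.
- *That one particular end date for AE person-time is clearly right.* The last-contact list in SAP 9.5 does not include the chart review, so event-free time may stop early. The second chart review, however, is a data abstraction and not a patient contact (protocol section 6, footnote), so using it may add time in which nobody saw the patient.

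The point is still more than missing detail: it concerns a secondary safety objective, and the remedy is cheap.

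**What to change.** 1. Keep the n (%) tables and add the number of events to the SOC/PT tables.
2. For the selected AEs of protocol 9.1.2.2, overall and by prior-DMT group, add: patients with a first event; person-years from Day 1 to the earliest of first event, death or a stated end of observation; and the rate per 100 person-years. If confidence intervals are shown, use the exact Poisson 95% interval that the SAP already adopts for the relapse rate.
3. State the end-of-observation date used for AEs. If it differs from the last-contact date used for the relapse rate, justify the difference.
4. If a proportion is what is meant, or the event count is dropped on purpose, correct SAP section 7 to declare the change and the reason. If rates are given for the selected AEs only, section 7 should also record that the protocol's rates by SOC and PT have been narrowed.

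Cost: an event column, one short rate table and one derived date. The AE date rules and the Poisson method are already in the SAP. The main drawback is wide intervals in the prior-DMT groups. The documents give no group sizes, but the minimum of 90 patients over four groups averages 90 / 4 = 22.5. The alternative under item 4 costs a sentence or two.

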15.1.1 All Adverse Events

The AEs will be summarised using the latest version of MedDRA PT as event category and MedDRA primary SOC body term as body system category.

Incomplete AE-related dates will be handled as specified in Section 9.10.

The following tables will be created:

- TEAE summary table with the number and percentage of patients that have:
 - TEAE
 - TEAE of Special Interest (TEAESI)
 - Grade 3 Lymphopenia
 - Grade 4 Lymphopenia
 - Herpes infections
 - Serious/opportunistic infections
 - Malignancies
 - TEAE leading to death

- TEAE leading to cladribine dose reduction
- TEAE leading to cladribine dose increase
- TEAE leading to cladribine temporary interruption
- TEAE leading to cladribine permanent discontinuation
- TEAE not recovered/resolved
- Any serious TEAE:
 - TEAESI
 - Leading to death
 - Leading to cladribine dose reduction
 - Leading to cladribine dose increase
 - Leading to cladribine temporary interruption
 - Leading to cladribine permanent discontinuation
 - Not recovered/resolved
- Cladribine-related TEAE:
 - TEAESI
 - Serious
 - Leading to death
 - Leading to cladribine dose reduction
 - Leading to cladribine dose increase
 - Leading to cladribine temporary interruption
 - Leading to cladribine permanent discontinuation
 - Not recovered/resolved
- The number and percentages of patients with TEAE by Primary SOC and PT
- The number and percentages of patients with TEAESI by Primary SOC and PT
- The number and percentages of patients with serious TEAE by Primary SOC and PT
- The number and percentages of patients with TEAE related to cladribine by Primary SOC and PT

TEAESI will be individuated using standardized and/or customized MedDRA queries that will be shared by Merck safety department using the dictionary version available at the time of the final analysis data-cut.

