- Selected adverse events: Reporting of AEs once informed consent has been obtained (as described in [Section 11](#)), with special focus on:
  - grade 3 lymphopenia
  - grade 4 lymphopenia
  - herpes infections
  - serious infections (infections for which a hospitalisation is initiated or extended), opportunistic infections (new onset or reactivation of latent infection)
  - malignancies.

For each AE, the start date, end date, classification of serious or non-serious, and outcome should be reported.

Derived and transformed data needed for the analysis are described in [Section 9.7.2](#).

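### The SAP summarises serious infections and opportunistic infections in one combined row, so neither protocol safety outcome gets its own figure and opportunistic infections have no patient count in any planned table

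*SAP*

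**What the plan says.** Protocol 9.1.2.2 introduces the safety outcomes with "Rates of selected, identified, and potentially clinically important AEs, including" and then gives six bullets. Two of them are "serious infections (infections for which a hospitalisation is initiated or extended)" and "opportunistic infections (new onset or reactivation of latent infection)". The Outcomes part of the protocol abstract lists them separately as well. Protocol 9.1.2.2 asks for these events overall and by prior-DMT subgroup, and protocol 11.2 ties the final report to that list.

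Protocol 9.3 (Variables) is laid out differently. One bullet holds both types, "serious infections (infections for which a hospitalisation is initiated or extended), opportunistic infections (new onset or reactivation of latent infection)", but each is still named and defined.

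In the special-interest block of its TEAE summary table, SAP 15.1.1 gives grade 3 lymphopenia, grade 4 lymphopenia, herpes infections and malignancies a row each. The remaining two outcomes share the row "Serious/opportunistic infections". SAP section 7 states that nothing has changed from the protocol's planned analyses.

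**The concern.** The two outcomes are defined on different axes. One depends on a consequence of the infection (hospital admission or a longer stay), the other on its nature (new onset or reactivation of a latent infection). An event can meet either definition, both or neither, so a count of patients with at least one of them answers neither question.

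The distinction matters for this product. Protocol 7.2 describes sustained reduction of T and B lymphocytes, and protocol 7.3 treats real-world safety, including in patients who previously had high-efficacy therapies, as an open question. The prior-DMT breakdown is where a reader would look for opportunistic infections. It divides a study of about 200 patients, possibly as few as 90, into four groups.

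**Working it through.** No stated figure is at issue, so the check asks what each planned output yields for each outcome.

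**Planned outputs (SAP 15.1 and 15.1.1)**

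| Output | Serious infections | Opportunistic infections |
|---|---|---|
| Combined summary row | Not separate | Not separate |
| "The number and percentages of patients with serious TEAE by Primary SOC and PT" | Approximate patient count from the infections SOC row | No category |
| "The number and percentages of patients with TEAESI by Primary SOC and PT" | Pooled with other special-interest terms | Pooled with other special-interest terms |
| All TEAEs by SOC and PT | Not split by seriousness | Individual PTs visible, no category total |
| AE listings | Hand count possible | Hand count possible |

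**Why the serious-infection figure is approximate.** The SAP states "Each participant will be counted only once within each SOC or PT", so the infections SOC row of the serious-TEAE table is a true patient count. But seriousness under protocol 11.1 goes beyond hospitalisation: it also covers, among others, life-threatening and medically important events. The row can therefore include patients who do not meet the protocol's definition of a serious infection.

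**Why the opportunistic figure is missing.** In the special-interest table, herpes, serious and opportunistic infections can all fall in the same SOC, so the SOC row does not isolate the last group. Adding up PT rows does not give patients either, because a patient with two PTs appears in both.

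**What the tables allow by subtraction.** Let U be the patients in the combined row, S those with a serious infection and O those with an opportunistic infection. Since U counts patients with either type, U − S ≤ O ≤ U. The documents give no expected counts, so those below are assumed.

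| U | S | Range of O (patients) | Of 90 | Of 200 |
|---|---|---|---|---|
| 4 | 2 | 4 − 2 = 2, to 4 | 2.2% to 4.4% | 1.0% to 2.0% |
| 8 | 5 | 8 − 5 = 3, to 8 | 3.3% to 8.9% | 1.5% to 4.0% |
| 12 | 8 | 12 − 8 = 4, to 12 | 4.4% to 13.3% | 2.0% to 6.0% |

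The bounds assume that S from the serious-TEAE table matches the serious part of the combined row. Without S, all that is known is that O lies between 0 and U.

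**The case against.** Four points can be made for the plan.

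- **The grouping has a source in the protocol.** Protocol 9.3 puts both types in one bullet, and the SAP row may simply follow it. That probably explains the row but does not justify it. Section 9.3 describes what is collected and still names and defines two things; the outcomes section lists two, and protocol 11.2 points to that section for reporting.
- **Other outputs carry much of the information.** This largely stands. A reader might infer from the combined row that the two outcomes go unreported, or that no other table helps to separate them. The documents do not support either inference: both types are reported in combined form, and serious infections can be recovered approximately.
- **Opportunistic events are not hidden.** A reader might also infer that a rare opportunistic infection would be lost among commoner hospitalised infections. It would not be. A single case would show as its own PT in the all-TEAE table and in the listings, and in the special-interest table if the queries capture it. What is lost is the category count, not sight of the event. Listings permit a hand count, but that does not replace a planned summary of a secondary outcome.
- **The queries are not shown.** SAP 15.1.1 leaves the MedDRA queries to the sponsor's safety department, so they may already be separate for the two types. If so, the split is easier to make, but the table as specified still has one row.

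The study is also descriptive and tests no hypothesis, which limits the consequence to clarity of reporting.

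**Conclusion.** The point holds in a limited form. The SAP merges two protocol secondary safety outcomes into one row without declaring it. Serious infections then have only an approximate figure, on wider criteria than the protocol's. Opportunistic infections have no patient count in any planned table, and subtraction can only bound it: 3 to 8 patients in the middle example. That example rests on assumed counts and on the two tables treating serious infections alike.

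This should be corrected because it concerns a stated secondary outcome and is inexpensive to put right. It has no bearing on the annualised relapse rate or any other effectiveness analysis. Whether these events should be given as rates or as percentages is a separate matter that this point does not address.

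**What to change.** Replace the combined row in SAP 15.1.1 with two rows, overall and by prior-DMT group, and let a patient count in both:

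- **Serious infections**, on the protocol's hospitalisation definition if the eCRF records hospitalisation for each event. If it does not, use the serious flag within the infections SOC and say so in the table footnote and in SAP section 7.
- **Opportunistic infections**, identified by their own MedDRA query, named in the SAP or in the document that supplies the queries.

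Bring the bullet in protocol 9.3 into line with 9.1.2.2 at the next opportunity. If the sponsor prefers to keep the combined row, declare it in SAP section 7 as a change, with the reason.

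The cost is one more row and one more query, plus a check of the eCRF. That check is needed: among the items protocol 9.3 requires for each AE, the only one on seriousness is whether the event was serious. It does not ask which criterion was met, so the hospitalisation definition may not be usable as written.
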